Two-arm, assessor blind, randomised controlled trial recruiting 348 older adults using a GP invitation letter (85%) or from community groups (15%). The Walk with Me intervention is a 12-week peer-led walking intervention based on social cognitive theory comprising three stages. Stage 1 (weeks 1–4) involves the participant setting initial pedometer step goals. Stage 2 (weeks 5–8) involves setting short- and long-term physical activity goals. Finally, stage 3 (weeks 9–12) emphasises behaviour rehearsal and practice and signposting participants to other activity programmes in their community. Participants in the control group will receive information on active ageing and healthy nutrition. The study will target community-dwelling older adults, aged 60 years or over living in areas of socio-economic disadvantage, defined as the most disadvantaged quartile of electoral wards in Northern Ireland. Trained peer mentors (n=35) will deliver the intervention. These are nonprofessional individuals who are similar to the target population, but sufficiently physically active. The primary outcome is the mean between-group change in accelerometer measured moderate-to-vigorous physical activity at 12 months from baseline, powered to detect 50 mins/week difference in moderate-to-vigorous physical activity. Secondary outcomes include SF-12; EQ-5D-5L; Warwick-Edinburgh Mental Well-Being Scale; blood pressure, body mass index and waist circumference; adverse events. In addition, focus groups with 30 intervention participants and their mentors at 12-weeks (post-intervention) and 6 months about their experiences. The primary economic outcome will be incremental cost per quality adjusted life year (QALY). We will assess the potential benefits and return on investment via cost-consequence analysis, within-trial cost-utility analysis and a long term model. Using intention-to-treat approach, we will compare the primary outcome between groups within a generalized linear mixed model including mentor as a random effect.

Background

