Individuals allocated to the control group will be contacted by a health improvement officer based at the Institute for Public Health. They will be thanked for their participation and informed that they will be contacted at 12 weeks, 6 months and 12 months for follow-up assessments. They will be given a copy of the Public Health Agency's information booklets on active ageing (Appendix 13) and healthy eating (Appendix 14). They will not receive any additional physical activity support over the course of the research study. To encourage retention, they will be contacted again by a health improvement officer at nine months to confirm contact details. Participants in the intervention group will be contacted at the same time to encourage retention. After the final data collection point, they will be given the opportunity to discuss with a member of the research team the availability of local physical activity opportunities (e.g. local walking groups). In line with approaches used in our pilot study¹⁸ and other interventions in older adults,¹³ they will also be offered a pedometer and physical activity diary during this meeting.

Outcome Measures

Demographic and outcome measures will be measured across four time points, as presented in Table 2.

Table 2: Outcome assessment according to the Walk with Me logic model and pilot study.

Data Collection	Baseline	3M	6M	12M
Socio-demographic: age, sex, marital status, car ownership (Appendix 15)	✓			
Actigraph accelerometer	✓	✓	✓	✓
Anthropometry – weight, body mass index (BMI), waist circumference	✓	✓		✓
Resting blood pressure	✓	✓		✓
Short physical performance battery (SPPB) ⁴⁰	✓	✓		✓
Warwick-Edinburgh Mental Well-Being Scale (WEMWBS) ⁴¹⁻⁴² (Appendix 16)	✓	✓		✓
EQ-5D-5L questionnaire ⁴³ (Appendix 17)	✓	✓		✓

UCLA Loneliness Scale ⁴⁴ (Appendix 18) and the Lubben Social Network Scale ⁴⁵ (Appendix 19)	✓	✓		✓
Physical activity self-regulation scale ⁴⁶ (Appendix 20)	✓	✓		✓
Physical activity and social activity self-efficacy ⁴⁷ (Appendix 21)	✓	✓		✓
Physical activity and social activity outcome expectancy ⁴⁸ (Appendix 22)	✓	✓		✓
Service use questionnaire (Appendices 23-25)	✓	✓		✓
Unintended consequences or adverse events		✓		✓

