The primary outcome will be daily minutes of moderate-to-vigorous physical activity per day (>1951CPM) at 12-months,⁴⁹ measured using a waist-worn Actigraph wGT3X+ accelerometer (ActiGraph, LLC, Pensacola, FL, USA) and worn for a minimum of four days out of seven.⁵⁰ To be included in the analysis, standard cleaning rules will be applied (at least five valid days defined as 600 minutes of wear time per calendar day).⁵¹ Non-wear time will be defined as a run of zero counts lasting > 60 minutes.

Secondary outcomes, which were found to be acceptable and feasible in our pilot study, were measures of mental well-being, using the Warwick–Edinburgh Mental Well-being Scale (WEMWBS),⁴¹⁻⁴² and quality of life using the EuroQol-5 Dimensions, five-level version (EQ-5D-5L) questionnaire.⁴³

In our logic model (Appendix 26) we define physical activity and social activity self-efficacy (10-point Likert scale, rating confidence in the ability to remain physically or socially active despite circumstances such as bad weather, boredom and pain),⁴⁷ and physical activity and social activity outcome expectancies (five-point Likert scale rating likelihood of outcomes such as good health, improved appearance, reduced stress, companionship and motivation),⁴⁸ as intermediate outcomes and possible mediators of the intervention, to aid the understanding of the mechanisms through which the intervention works as part of the process evaluation. We will also assess physical activity self-regulation (PASR),⁴⁶ as it indicates the processes through which change is hypothesised to occur. The PASR questionnaire assesses the use of BCTs included in the intervention such as self-monitoring, goal setting and social support. In addition, loneliness and social engagement will be measured with the UCLA Loneliness Scale⁴⁴ and the Lubben Social Network Scale.⁴⁵ As requested by participants in the pilot study, we will also measure resting blood pressure, height, weight, body mass index (BMI) and waist circumference, as these have been shown to be associated with increased physical activity in

older adults.⁵² Physical functioning will also be measured using the short physical performance battery (SPPB).⁴⁰ Light intensity physical activity (>100 & ≤1951 CPM) and sedentary behaviour per day (≤100 CPM) will be calculated from the accelerometer data.

Health economic evaluation

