following participant feedback accordingly. Standard unit costs will be used to cost resources. Responses to the EQ-5D-5L at baseline, 12 weeks and 12 months will be converted to utilities using the tariff recommended by NICE at the time of analysis.⁵⁸ We will use the area under the curve method to calculate QALYs.⁵⁹ To deal with missing data, we will explore the quantity of missing data and report on the missing rates for the different cost components and outcomes, by study group. We will also explore the nature of the missing data.

Since the relatively short time horizon of the trial will not capture the potential long-term health impact of the intervention, trial data will be incorporated into a long-term economic model with a lifetime horizon. We will conduct a literature review prior to designing the model to ensure we have the most up to date data on lifetime disease incidence, utilities and costs related to physical activity. The model is most likely to be a Markov state-transition model as these are particularly useful for modelling lifetime costs and health outcomes and have been used previously to assess the long-term cost-effectiveness of other physical activity interventions.⁶⁰⁻

⁶³

For both within trial and long term analyses we will perform deterministic sensitivity analysis to explore key assumptions and probabilistic sensitivity analysis (PSA)⁶⁴ to account for uncertainty arising from imprecision in the economic data. The PSA will generate bootstrapped replications of the incremental cost effectiveness ratio which will be plotted on the cost-effectiveness plane and used to construct a cost-effectiveness acceptability curve: this will depict the probability of the Walk with Me intervention being cost-effective compared to usual care at different willingness-to-pay per QALY thresholds. We will consider the performing subgroup analyses and this will be in keeping with the main statistical analyses. A detailed health economic analysis plan will be written in advance.

Methods for data collection

Outcome measures will be assessed at baseline, post-intervention (12 weeks from the start of the intervention in the intervention group or equivalent timing for the control group), 6 months (accelerometer only) and 12 months after baseline, in person, by a Research Assistant, who will be blind to group allocation.

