Outcome measures will be collected at the participant's home, at a local community centre/venue, or their general practice if the participant would prefer. The meeting will adhere to COVID-19 public health and social measures that are in place at the time, such as wearing face coverings and physical distancing.

Participants will be asked to complete self-reported questionnaires (Appendices 15-25), with support from the Research Assistant if needed. When these are complete, resting blood pressure will be measured using an Omron M6 digital sphygmomanometer. In line with the American College of Sports Medicine guidelines, blood pressure will be recorded after the participant has been seated for at least five minutes, and measured twice, separated by at least one minute, and averaged.⁶⁵

Weight will be measured using a Seca weight scale and height measured using a portable stadiometer, and used to calculate body mass index. Waist circumference will be measured as the midpoint between the lowest rib and the iliac crest, using a fibre glass tape.

The SPPB includes three tests of balance and gait:

1) *Chair Rise Test*

For the chair stand test, whilst seated, the participant is asked to stand up and sit down as quickly as possible five times, without stopping. Whilst completing this, the participant should keep their arms folded across their chest. The movement will first be demonstrated by the Research Assistant. Timing, using a digital stopwatch, begins as soon as the participant bends forward at the hips, and ends when they sit back down after completing the fifth stand. The test is stopped if the participant starts to use their hands, or after one minute if they have not completed 5 rises, and if the Research Assistant is concerned about the participant's safety. If the test is stopped early, the time is recorded and the number of chair rises completed, along with the reason for stopping the test. If the participant is unable to complete 5 chair rises, they are given a score of 0 points. If they complete 5 chair rises in 16.70 seconds or more they score 1 point; in 13.70 to 16.69 seconds they score 2 points; in 11.20 to 13.69 seconds they score 3 points; and in 11.19 seconds or less they score 4 points.

2) *Standing Balance Test*

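### At 12 weeks and 12 months the blinded Research Assistant may help with questionnaires that can hint at the arm before recording the SPPB and waist circumference

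*Protocol*

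**What the plan says.** The Protocol summary calls the study a "Two-arm, assessor blind, randomised controlled trial". Under Methods for data collection, outcomes are assessed "in person, by a Research Assistant, who will be blind to group allocation".

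The same section sets out the visit. Participants fill in the self-reported forms (Appendices 15-25) "with support from the Research Assistant if needed. When these are complete, resting blood pressure will be measured", with a digital device. Weight, height, waist by tape and the three SPPB tests are then described, and the accelerometer is fitted after the tests.

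Two of the forms matter here:

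- **Self-regulation scale (PASR).** Table 2 lists it as Appendix 20, at baseline, 3 months and 12 months. Under Outcome Measures: "The PASR questionnaire assesses the use of BCTs included in the intervention such as self-monitoring, goal setting and social support".
- **Service-use questionnaire.** Table 2 lists it as Appendices 23-25, at the same visits. The Health economic evaluation section says that it covers use of leisure services.

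On rest before blood pressure, the Protocol asks that "blood pressure will be recorded after the participant has been seated for at least five minutes".

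**The concern.** An assessor who helps someone answer items on self-monitoring, goal setting and social support, or on leisure services, may hear something that points to the arm. The intervention consists of pedometer monitoring, weekly goals, a peer mentor and signposting to local activities. Controls receive two booklets and no further activity support during the study, and are offered a pedometer only after the final data collection.

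If this happens early in the visit, the measures that depend most on the assessor are taken by someone who is no longer blind. In the SPPB the assessor times the chair rise by stopwatch, judging the start and end by eye, and may stop that test on a safety concern. Waist circumference depends on where and how the tape is placed.

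Both are secondary outcomes of some weight. The secondary research question names physical function and cardiovascular risk factors, secondary objective 2 lists waist circumference, and physical functioning enters the cost-consequence analysis.

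**Working it through.** No arithmetic applies. The check sets the Protocol's statements side by side.

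1. **Is it the same person?** Yes. Methods for data collection names one role, the Research Assistant, for outcome assessment, for help with questionnaires and for the SPPB.

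2. **Are the revealing forms in the set completed first?** Yes. That set is Appendices 15-25. PASR is Appendix 20 and the service-use questionnaire is Appendices 23-25. Self-efficacy (Appendix 21) and outcome expectancy (Appendix 22) are also in it. The adverse-event proforma (Appendix 32) is not, and its place in the visit is not given.

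3. **Is the order stated?** Only in part:
   - Blood pressure is stated to follow the questionnaires.
   - Weight, height, waist and SPPB come next in the description, with no explicit word of sequence. Their order is implied.
   - The accelerometer is stated to come at the end.

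4. **At which visits can it matter?**
   - Baseline: no. Under Randomisation, allocation follows the baseline measures.
   - 6 months: no. That visit is accelerometer only.
   - 12 weeks and 12 months: yes. Questionnaires, waist and SPPB are all scheduled in Table 2.

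5. **Which outcomes are exposed?**
   - Primary outcome (accelerometer minutes of activity): recorded by a device over the days after the visit and not scored by the assessor.
   - Blood pressure: read by a digital device, so scoring bias is unlikely.
   - SPPB and waist: recorded by the assessor, hence exposed.

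6. **Does blood pressure need the questionnaires first?** No. The requirement is five minutes seated, which does not depend on finishing the whole set.

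7. **Is there another safeguard?** The body text names no separate helper, no request that participants keep their group to themselves and no record of unblinding. The appendices are not shown and may contain such an instruction. It would lessen the risk but would not change the order described.

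**The case against.** The strongest case on the other side has five parts.

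- **Help is occasional and the clue is weak.** The forms are self-completed, with help only where needed, by people who communicate in English and score 24 or more on the Mini-Mental State Exam. PASR is given to both arms. Controls receive an active-ageing booklet and may also set goals or monitor themselves. This stands. A reader might infer that the assessor will probably learn the arm, or that the order removes blinding. The Protocol supports neither, only that blinding may be lost.
- **The order of waist and SPPB is not fixed.** This stands as a limit. The order of description is nevertheless what an assessor would naturally follow, and nothing in the text directs otherwise.
- **Questionnaires first is a defensible choice.** Moving every form to the end would put EQ-5D-5L, which feeds the QALY, and WEMWBS after a physical performance test that might colour the answers. This stands against a full reversal, but not against moving only the revealing forms.
- **Reordering is only a partial remedy.** An assistant unblinded at 12 weeks who returns at 12 months stays unblinded, and a participant can mention a mentor at any time. This stands, and it is why a log is needed as well.
- **Nothing is misstated.** The Protocol commits to a blind assessor, and the concern identifies only a possible leak. That is fair. It makes this a suggested improvement, not an error.

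**Conclusion.** The point holds in a narrow form. At 12 weeks and 12 months, the described visit order allows the blinded assessor to help with forms that can hint at allocation before recording the two most assessor-dependent outcomes, SPPB and waist. The primary outcome and blood pressure are unlikely to be affected.

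The size cannot be estimated. SPPB bands change by a whole point across 0.01 s (13.69 against 13.70 seconds for the chair rise), and a reader might infer a bias of calculable size from that. Sharp cut-points belong to any banded score and are not evidence of bias. A figure would need the share of participants helped, the share of those who reveal their arm, the share close to a cut-point and the share then mis-scored. The Protocol gives none of these.

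The conclusion assumes that visits follow the order of description and that the unseen appendices do not direct otherwise. It is a low-priority, inexpensive improvement.

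**What to change.** Amend the visit description in Methods for data collection to state this order:

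1. EQ-5D-5L and WEMWBS at the start.
2. Blood pressure after five minutes seated, then weight, height and waist, then SPPB.
3. Only then the self-regulation, self-efficacy, outcome-expectancy, service-use and adverse-event forms.
4. Accelerometer fitting last, as now.

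The loneliness and social network scales could go in either group, but the text should say which.

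Add one item for the Research Assistant to complete at the end of each visit: whether allocation was revealed. The 12-month SPPB and waist results can then be examined with previously unblinded cases identified.

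Cost: a changed paragraph, matching assessor instructions and one recorded item, with no extra staff or procedures. The visit order becomes slightly more complex, and some process questionnaires follow a short physical test. The change does not prevent carry-over if the same assistant was unblinded at 12 weeks, but the log would show where that occurred.

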- Able to communicate in English and living independently in the community (i.e. at home). This will include those residing in independent living facilities that meet the threshold for participation, but not those in institutions such as care homes. We will also only include individuals planning to stay in their current accommodation during the next year, to try and ensure they will be available for follow-up assessment.
- For individuals not in employment at the outset, they will be included as long as they are not planning on returning to work over the following 12 months. This is to mitigate against the potential interaction between returning to work and the outcome measures, which was observed in the pilot study.
- Males or females aged 60 years or over.
- To screen participants' competency to give informed consent, we will use the Mini-Mental State Exam.²⁰ This is an assessment of cognitive function, including attention and orientation, memory, registration, recall, calculation, language and ability to draw a complex polygon. Lower scores indicate more severe cognitive problems, and we will only include participants who score 24 or higher, as this indicates 'normal' cognitive function.²⁰ We will also screen for frailty using the PRISMA-7 questionnaire.²¹ Individuals scoring three or more will be excluded.

- Only those who are not currently physically active, according to the current physical activity recommendations,³ will be included. This will be assessed using the General Practice Physical Activity Questionnaire,²³ which is designed to screen inactive individuals and takes approximately 30 seconds to complete. Individuals classified as inactive, moderately inactive or moderately active will be eligible for inclusion.
- Individuals who report no recent medical history in the last six months that would limit ability to participate in a walking programme will be included. This will be assessed using the Physical Activity Readiness Questionnaire,²⁴ which is commonly used in physical activity programmes to limit the potential of adverse events occurring. Typically, individuals who would not be eligible due to their recent medical history require a tailored rehabilitation programme.

[figure not shown]
The exclusion criteria are:

- Individuals who do not meet the inclusion criteria
- Individuals who decline to participate
- Individuals with learning disabilities will be excluded
- Individuals unwilling to give informed consent

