This test assesses the participant's ability to stand unaided for 10 seconds with their feet in three different positions. After demonstrating these positions (Figure 3), the participant is first asked to stand unsupported, feet together for 10 seconds. They are permitted to use their arms, bend their knees, or move their body to maintain their balance, but they will be asked to try to not move their feet. The research assistant stands next to the participant, allowing them to hold onto their arms to get their balance. Timing begins when the participant has their feet together and let's go of the supporting arm. If they can complete the 10 seconds, they progress to the semi-tandem stand. In the semi-tandem stand, the participant is asked to stand for up to 10 seconds with the heel of one foot placed by the big toe of the other foot. If they complete the semi-tandem stand, the participant completes the final balance test, the

full tandem stand. In this, one foot is placed directly in front of the other. The time balance is maintained for each test is recorded, to a maximum of 10 seconds. For each balance test not completed, a participant is given 0 points. If they hold the feet together and the semi-tandem balance for at least 10 seconds, they score 1 point each. If they hold the full tandem balance for at least 10 seconds, 2 points are awarded.

Figure 3: Feet Positions for Standing Balance Test

3) Usual walking speed

A distance of 3 metres is measured with a tape measure and a marker cone is placed at either end. The participant is asked to walk at their normal walking speed between the two cones and the time taken to complete the walk is recorded. The participant is allowed to use a walking aid if they normally use one when walking. The test is repeated twice and averaged. One point is awarded if the average time across the two tests is more than 6.52 seconds. Two points are awarded if the time is between 4.66 and 6.52 seconds; three points are awarded if the time is between 3.62 and 4.65 seconds, and four points are awarded if the time is <3.62 seconds.

At the end of the test period, participants will be fitted with an accelerometer and given an instructional guide on how to use it (Appendix 27) and a diary to record wear time (Appendix 28). They will be asked to wear the accelerometer during waking hours for 7 days. A pre-paid envelope will be provided to return the accelerometer to the study team.

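### The SPPB scoring rules risk a ceiling on gait and cannot credit a partial tandem hold; usual gait speed should be prespecified beside the total

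*Protocol*

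**What the plan says.** Under Outcome Measures, the SPPB is the one instrument named for physical functioning. Table 2 schedules it at baseline, 3 months and 12 months. Physical function at 12 months is part of the secondary research question and is listed among the consequences in the cost-consequence analysis.

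Methods for data collection fixes the scoring of each component:

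- **Gait.** "A distance of 3 metres is measured with a tape measure and a marker cone is placed at either end". Two timed walks at normal speed are averaged. A mean time above 6.52 s scores 1, one of 4.66 to 6.52 s scores 2, and one of 3.62 to 4.65 s scores 3. The top band is worded: "four points are awarded if the time is <3.62 seconds".
- **Balance.** Feet together, semi-tandem and full tandem are attempted in that order, each only after the one before has been held for 10 s. The first two are worth 1 point each. "If they hold the full tandem balance for at least 10 seconds, 2 points are awarded". A test not completed scores 0. "The time balance is maintained for each test is recorded, to a maximum of 10 seconds".
- **Chair rise.** Scored 0 to 4 from the time for five rises. The top band is 11.19 s or less, and anyone unable to complete five rises scores 0.

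On the PRISMA-7 frailty screen, Eligibility Criteria states: "Individuals scoring three or more will be excluded". People with recent medical history that would limit a walking programme are also kept out. Data management and statistical analysis says that secondary outcomes will be handled by methods similar to the primary. It does not say whether the SPPB total, its components or the recorded times will be analysed.

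**The concern.** Two features of the written scoring rule limit what the SPPB can show.

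First, once a participant covers 3 m in under 3.62 s, no further gain in walking speed can change the gait score. The intervention is a walking programme, and entry excludes people with frailty or recent limiting illness, so a sizeable share of participants may already be in that band at baseline.

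Second, the balance rule has a hole at 3. A full tandem held for 9.9 s scores the same as one not held at all, and another 0.1 s is worth 2 points. Hold time is recorded, but no scoring rule uses a partial hold.

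Because no other measure of physical function is named, a flat SPPB result at 12 months would be hard to read: it could mean no effect, or partly an effect that the bands could not register. If the choice between points and times is left until the data are seen, it also becomes a post hoc choice.

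**Working it through.** The protocol states no power, baseline mean or expected effect for the SPPB, so there is no figure of its own to reproduce on this point. Its primary sample size does reproduce: 133 × 1.04 = 138.3, giving 139 per group; 139 / 0.80 = 173.75, giving 174; 2 × 174 = 348. The 139 is used below only as a convenient group size.

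**1. Gait bands as speeds** (speed = 3 m / time; cut-offs from Usual walking speed)

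- 3 / 6.52 = 0.460 m/s
- 3 / 4.65 = 0.645 m/s
- 3 / 3.62 = 0.829 m/s, the start of the 4-point band

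**2. Attainable balance scores** (rules from Standing Balance Test)

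- Feet together not held: 0
- Feet together held, semi-tandem not: 1
- Both held, full tandem not: 1 + 1 = 2
- All three held: 1 + 1 + 2 = 4

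A score of 3 cannot occur. The step from 2 to 4 is 2/12, one sixth of the SPPB maximum, and turns on a single 10 s threshold. Chair rise runs 0 to 4 and gait 1 to 4, so every total from 1 to 12 is still attainable.

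**3. Share already at the gait maximum**

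Assumption: baseline usual gait speed is normal. The means and SDs are mine, because the protocol gives none. Share = 1 − Φ((0.829 − mean) / SD). For example, at mean 0.9 and SD 0.20: 1 − Φ(−0.356) = 0.64.

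| Mean (m/s) | SD 0.15 | SD 0.20 | SD 0.25 |
|---|---|---|---|
| 0.7 | 20% | 26% | 30% |
| 0.8 | 42% | 44% | 45% |
| 0.9 | 68% | 64% | 61% |
| 1.0 | 87% | 80% | 75% |
| 1.1 | 97% | 91% | 86% |
| 1.2 | 99% | 97% | 93% |

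**4. What the bands cost for a given gain**

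Further assumptions: a true mean difference of 0.10 m/s, SD 0.20 m/s, 139 per group, two-sided 5% t-test, no baseline adjustment. On speed, the standardised effect is 0.10 / 0.20 = 0.50 and power is 99%. On points, the effect is the difference in mean points divided by the pooled SD of points. The relative sample size is (0.50 / effect on points)².

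Worked case, control mean 1.0 m/s: the chances of being below the three cut-offs are 0.0035, 0.0377 and 0.1959, so mean points are 4 − 0.2371 = 3.763, with variance 0.270. At 1.1 m/s they are 0.0007, 0.0114 and 0.0875, so mean points are 3.900, with variance 0.115. The pooled SD is √((0.270 + 0.115)/2) = 0.439, the effect is 0.137 / 0.439 = 0.31, and the relative sample size is 2.55.

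| Control mean (m/s) | Effect on points | Relative sample size | Power on points |
|---|---|---|---|
| 0.7 | 0.46 | 1.17 | 97% |
| 0.8 | 0.43 | 1.34 | 95% |
| 0.9 | 0.38 | 1.71 | 89% |
| 1.0 | 0.31 | 2.55 | 74% |
| 1.1 | 0.23 | 4.57 | 49% |

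With SD 0.25, power on speed is 91%; on points it falls from 86% at mean 0.7 to 48% at mean 1.1. Points are less efficient than speed at every mean tried. Only the size of the loss depends on the baseline.

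**The case against.** The strongest reply is that the protocol gives a scoring rule, not an analysis rule. Nothing bars analysing the recorded times, and the analysed variable may be set in an SAP that is not shown. That stands. A reader might infer that the times are discarded; the protocol does not say so. What remains is that it fixes the points and does not commit to the times.

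A reader might also infer that most improvement would be invisible. The documents do not support this. They hold no baseline gait or SPPB data, and the share at the gait maximum runs from 20% to 99% over the assumed range. Even at a mean of 1.0 m/s, a 0.10 m/s gain still shows as an effect of 0.31 on points against 0.50 on speed, which is attenuation. Nothing has been calculated for chair rise, which supplies a third of the maximum score.

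Nor is it shown that the sample sits at the top of the scale. The frailty and illness screens push that way, but entry is also limited to people who do not meet activity recommendations, from the most disadvantaged quartile of wards, with no upper age limit, and walking aids are allowed in the gait test. The step goal in the intervention section, 500 steps in roughly 5 minutes, does not settle it: it is a conversion for extra activity, not a usual speed over 3 m, and needs an assumed step length.

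The hole in the balance score is not a ceiling, since 4 is reachable. It hides only partial tandem gains. Any threshold separates 9.9 s from 10 s; what is particular here is that the step is worth 2 points with nothing between.

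Finally, replacing points by raw times has a cost. Five-rise time does not exist for people who cannot complete five rises, whom the score keeps at 0, and remote visits may lack some components. This is a reason to keep the SPPB total and add to it.

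**Conclusion.** The point holds as a risk of ceiling and a loss of resolution in one secondary outcome. Two parts follow from the text without any assumption: the gait score is at its maximum from 0.83 m/s, and balance can take only 0, 1, 2 or 4.

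The size of the gait problem is unknown. It rests on assumed normal gait speeds, and more than half the sample starts at the gait maximum only if the mean exceeds about 0.83 m/s. It would be going too far to say that a null SPPB result would reflect the scoring; it could do so in part. The case for adding gait speed does not depend on the baseline, because under these assumptions points lose efficiency at every mean tried, from a relative sample size of 1.17 at 0.7 m/s to 4.57 at 1.1 m/s. The primary outcome and its sample size are untouched.

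**What to change.** - Keep the SPPB total as planned, and prespecify usual gait speed (3 m divided by the mean of the two times) as a continuous secondary outcome beside it.
- Chair-rise performance may be added in a form that keeps people who cannot complete five rises, for example rises per second (5 divided by the time), set to 0 if unable.
- Check the balance rule against the instrument the protocol cites. Use the recorded tandem hold time so that a partial hold earns an intermediate score and the balance part can take the value 3. The threshold should come from the instrument, since the protocol gives none.
- Apply the same scoring in both arms and at all visits, and settle it before any unblinded data are seen.

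**Cost.** Wording in the outcome section and the analysis plan. Gait and balance times are already recorded and the chair rise is already timed, so no visit or test is added. The downside is one or two further secondary results to report. Components may also be missing at remote visits, where the protocol promises only as much of the SPPB as is feasible by video; the plan should say how those gaps are treated.
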